1.2. Schema

Figure 1: Schematic Overview of Study CNTO1959UCO2002

1.3. Schedule of Activities (SoA)

Table 1: SoA - Combination Comparison Phase (ie, through Week 12)									
	Phase	Screening	Treatment						
	Week	Within 8 weeks	W0	W2	W4	W6 ^e	W8	W10	W12 ^f
Study Procedures^{a,b,c,d}									
Screening/Administrative									
Informed consent (ICF) ^g		X							
ICF for optional pharmacogenomic sub-study ^g		X							
ICF for optional Week 4 endoscopy and biopsy sub-study ^g		X							
Review medical history requirements		X							
Inclusion/exclusion criteria ^h		X	X						
Demographics		X							
Prestudy therapy		X							
Preplanned surgery/procedure(s)		X							
QuantiFERON [®] -TB test ⁱ		X							
HBV and HCV testing		X							
HIV test		X							
Chest radiograph ^j		X							
Serum pregnancy test ^k		X							
Stool for enteric pathogens ^l		X							
Training on Mayo diary and BSFS diary completion ^m		X	X						
Study Intervention Administration									
Randomization			X						
Administer study intervention			X ^z	X	X	X	X	X	
Efficacy Evaluations									
Endoscopy ⁿ		X ^o			(X) ^p				X
Mayo score			X						X
Partial Mayo score		X		X	X	X	X	X	
BSFS			X	X	X	X	X	X	X
Patient-Reported Outcomes (PROs)^b									
IBDQ			X			X			X
PROMIS-29			X			X			X

Table 1: SoA - Combination Comparison Phase (ie, through Week 12)									
	Phase	Screening	Treatment						
	Week		W0	W2	W4	W6 ^e	W8	W10	W12 ^f
Study Procedures^{a,b,c,d}									
PROMIS Fatigue Short Form 7a			X				X		X
PGIC						X			X
Safety Evaluations									
Physical examination		X							X
12-lead ECG		X							
TB evaluation ^l /Other infection assessment ^l		X	X	X	X	X	X	X	X
Vital signs ^f		X	X	X	X	X	X	X	X
Weight		X	X						X
Height		X							
Urine pregnancy test ^k			X	X	X	X	X	X	X
Concomitant therapy review		X	X	X	X	X	X	X	X
Adverse events		X	X	X	X	X	X	X	X
UC-related emergency department visits, hospitalizations, and surgeries			X	X	X	X	X	X	X
Injection-site evaluation ^{bb}			X	X		X		X	X
C-SSRS ^s		X	X	X	X	X	X	X	X
Clinical Laboratory Tests									
Hematology and chemistry ^{aa}		X	X	X	X	X	X	X	X
CRP			X	X	X	X	X	X	X
Fecal calprotectin			X	X	X		X		X
Pharmacokinetics/Immunogenicity^t									
Serum guselkumab/golimumab concentration			X	X	X	X	X	X	X
Antibodies to guselkumab/golimumab			X	X	X		X		X
Pharmacodynamics and Biomarkers									
Biopsy (RNA, histology, single cell isolation) ^u		X ^v			(X) ^p				X
Serum biomarkers ^w		X		X	X				X
Whole blood (RNA) ^w		X		X	X				X
Whole blood (PBMC) ^{w,cc}		X			(X) ^p				X
Fecal biomarkers ^x			X	X	X				X
Pharmacogenomics									
Whole blood (DNA) ^y			X						

BSFS=Bristol Stool Form Scale; CRP=C-reactive protein; C-SSRS=Columbia-Suicide Severity Rating Scale; DNA=deoxyribonucleic acid; ECG=electrocardiogram; HBV=hepatitis B virus; HCV=hepatitis C virus; HIV=human immunodeficiency virus; IBDQ=Inflammatory

Table 1: SoA - Combination Comparison Phase (ie, through Week 12)								
	Phase	Screening	Treatment					
	Week	Within 8 weeks	W0	W2	W4	W6 ^c	W8	W10
Study Procedures ^{a,b,c,d}								

Bowel Disease Questionnaire; IV=intravenous; PBMC= peripheral blood mononuclear cell; PK=pharmacokinetic; PGIC=Patient’s Global Impression of Change (of Severity of UC); PRO=patient-reported outcome; PROMIS=Patient-Reported Outcomes Measurement Information System; RNA=ribonucleic acid; SC=subcutaneous; TB=tuberculosis; UC=ulcerative colitis; W=Week.
 
a. Screening should occur within 8 weeks before the W0 visit. Visit dates are based on the participant’s original randomization date; visit windows are as follows: day of the scheduled visit ±4 days (ie, plus or minus 4 days).
 
b. All assessments are to be completed before study intervention administration, unless otherwise specified; PRO assessments should be completed first. At the screening visit, the C-SSRS should be completed as the first assessment after signing informed consent and before any other tests, procedures, or other consultations. When blood samples are to be collected for safety, PK, efficacy, and biomarkers evaluations at the same time point, the order of blood draws will be samples for CRP, hematology and chemistry, PK/immunogenicity, serum biomarkers, whole blood DNA (for those participating in the optional pharmacogenomic sub-study at Week 0), and whole blood RNA.
 
c. Participants who discontinue study intervention (but have not terminated study participation) before W12 visit should complete the W12 assessments at the time of discontinuation and a safety follow-up visit (see Table 2) approximately 16 weeks after their last study intervention administration.
 
d. Subjects who terminate their study participation before the W12 visit should complete the W12 assessments at the time of termination (which will serve as the early termination visit).
 
e. For participants who are receiving oral corticosteroids, the investigator must begin tapering the daily dose of corticosteroids at W6.
 
f. Participants randomized to combination therapy will receive guselkumab monotherapy after W12. Participants randomized to a monotherapy group will continue on their originally randomized monotherapy after W12.
 
g. Must be signed before first study-related activity.
 
h. The required source documentation to support meeting the enrollment criteria are noted in Appendix 6 [Section 10.6], Regulatory, Ethical, and Study Oversight Considerations. Check clinical status again before first dose of study intervention.
 
i. All participants will undergo QuantiFERON[®]-TB testing. If the QuantiFERON[®]-TB test is not approved/registered in the country in which this protocol is being conducted or the tuberculin skin test is mandated by local health authorities, a negative tuberculin skin test result (see Appendix 3 [Section 10.3]) is also required. In Ukraine, while the QuantiFERON[®]-TB test is not approved/registered, it is accepted, and a tuberculin skin test is not required.
 
j. Chest radiograph (posterior-anterior and lateral views, or per country regulations where applicable) must be obtained within 3 months before the W0 visit. Note: A chest CT scan is also acceptable in place of a chest radiograph.
 
k. Must be performed before any study intervention administration for female participants of childbearing potential.
 
l. Stool studies for enteric pathogens may be performed at either the central or local laboratory and must include a stool culture and Clostridium difficile toxin assay. These tests must be performed during screening or have been performed during the current episode of disease exacerbation (as long as the stool studies were performed within 4 months before the first administration of study intervention). Additional testing (eg, ova and parasites or Escherichia coli O157:H7
								

Table 1: SoA - Combination Comparison Phase (ie, through Week 12)									
	Phase	Screening	Treatment						
	Week	Within 8 weeks	W0	W2	W4	W6 ^c	W8	W10	W12 ^f
Study Procedures ^{a,b,c,d}									

assessments) may be performed at the investigator’s clinical discretion.
 
m. Participants should be instructed to bring their diaries to each study visit for review.
 
n. Endoscopy findings will be assessed by the investigator (ie, local endoscopist) during the procedure and a video of the endoscopy must be submitted to the central reader.
 
o. The screening endoscopy must be performed within 2 weeks of the baseline (W0) visit. The interval from the endoscopy procedure to the availability of the Mayo endoscopy subscore is approximately 4 days; therefore, the screening endoscopy must be performed at least 4 days before the baseline (W0) visit. The Mayo endoscopy subscore obtained during the central review of the video endoscopy will be used to determine eligibility (ie, Mayo endoscopy subscore ≥ 2) and to calculate the baseline Mayo score. A full colonoscopy will replace a sigmoidoscopy if screening for polyps or dysplasia is required. At least 48 hours must elapse between a colonoscopy with polypectomy and the W0 visit.
 
p. Only those participants who consent to participate in the optional endoscopy and biopsy sub-study will undergo Week 4 endoscopy and mucosal biopsy collection and whole blood PBMC collection.
 
q. If TB is suspected at any time, a chest radiograph (or chest CT scan if obtained instead) and QuantiFERON[®]-TB test should be performed. In countries where the QuantiFERON[®]-TB test is not registered/approved or the tuberculin skin test is mandated by local health authorities, TB skin testing (see Appendix 3 [Section 10.3]) should also be performed. Note: In Ukraine, while the QuantiFERON[®]-TB test is not approved/registered, it is accepted and a tuberculin skin test is not required.
 
r. Temperature, pulse/heart rate, respiratory rate, and blood pressure. At a study intervention administration visit, vital signs should be obtained before, approximately every 30 minutes during, and twice (at approximately 30-minute intervals) after completion of the IV infusion(s), or before and approximately 30 minutes after the SC injection, or if the participant reports any symptoms.
 
s. At the screening visit, the C-SSRS should be completed as the first assessment after signing informed consent and before any other tests, procedures, or other consultations. For subsequent visits, the C-SSRS should be completed after all PROs and before any other tests, procedures, or other consultations.
 
t. For all visits where study intervention will be administered, 1 blood sample should be collected prior to study intervention administration for evaluation of serum concentrations and/or antibodies to interventions. In addition, for IV infusion-related visits (ie, Weeks 0, 4, and 8), another blood draw should be taken approximately 60 minutes after completion of the infusion for serum concentration measurement. All reasonable attempts should be made to collect samples at the scheduled timepoints and record the actual dates and times of PK sample collections.
 
u. Mucosal biopsy samples will be collected from all participants during endoscopy for RNA expression analysis, histologic assessment, and single cell isolation.
 
v. The screening biopsy samples for histology, RNA analyses, and single cell isolation will be collected from all participants during the screening endoscopy performed within 2 weeks of the baseline (W0) visit.
 
w. Serum biomarkers and whole blood RNA and PBMCs will be collected from all participants to evaluate the molecular
									

Table 1: SoA - Combination Comparison Phase (ie, through Week 12)								
Phase	Screening	Treatment						
Week	Within 8 weeks	W0	W2	W4	W6 ^c	W8	W10	W12 ^f
Study Procedures ^{a,b,c,d}								
effects of each study intervention in UC.								
x. Fecal biomarkers (including microbiome) and associated products will be collected from all participants to evaluate the association between microbial activities, study intervention, and/or UC.								
y. Whole blood for genetic analyses will be collected (where local regulations permit) only from participants who sign a separate ICF to participate in the optional pharmacogenomic sub-study. The pharmacogenomic (DNA) sample should be collected at the specified time point; however, if necessary it may be collected later without constituting a protocol deviation.								
z. For the baseline (W0) visit, the IV study intervention should be administered first. The SC study intervention should be administered approximately 30 minutes after the IV study intervention infusion is complete.								
aa. Certain laboratory abnormalities require re-testing and potential discontinuation of study intervention (See Sections 8.2.5 and 7.1, respectively).								
bb. An injection-site reaction is any adverse reaction at any SC study intervention injection site. Injection sites will be evaluated for reactions and any injection-site reaction should be recorded as an adverse event.								
cc. Whole blood (PBMC) samples are to be collected ideally within ± 2 days of the endoscopy visit.								

Table 2: SoA- Monotherapy Phase (ie, after Week 12)												
Phase	Treatment										Early Term^{c,e}	Safety Follow-Up^{d,e}
Week	W14	W16	W18	W22	W24	W26	W30	W32	W34	W38		
Study Procedure^{a,b}												
Study Intervention Administration												
Administer study intervention	X	X	X	X	X	X	X	X	X			
Efficacy Evaluations												
Endoscopy ^f										X	X	
Mayo score										X	X	
Partial Mayo score	X	X	X	X	X	X	X	X	X			
Patient-Reported Outcomes (PROs)^b												
IBDQ					X					X	X	
PROMIS-29					X					X	X	
PROMIS Fatigue Short Form 7a					X					X	X	
PGIC					X					X	X	
Safety Evaluations												
Physical examination										X	X	X
TB evaluation ^g /Other infection assessment	X	X	X	X	X	X	X	X	X	X	X	X
Vital signs ^h	X	X	X	X	X	X	X	X	X	X	X	X
Weight										X	X	X
Urine pregnancy test ⁱ	X	X	X	X	X	X	X	X	X	X	X	X
Concomitant medication review	X	X	X	X	X	X	X	X	X	X	X	X
Adverse events	X	X	X	X	X	X	X	X	X	X	X	X
UC-related emergency department visits, hospitalizations, and surgeries	X	X	X	X	X	X	X	X	X	X	X	X
Injection-site evaluation ^p	X	X	X	X	X	X	X	X	X	X	X	
C-SSRS ^j	X	X	X	X	X	X	X	X	X	X	X	X
Clinical Laboratory Tests												
Hematology and chemistry ^o	X	X	X	X	X	X	X	X	X	X	X	
CRP		X				X			X		X	
Fecal calprotectin						X				X	X	
Pharmacokinetics/Immunogenicity^k												
Serum guselkumab/golimumab concentration	X	X			X				X	X	X	X

Phase	Treatment										Early Term ^{c,e}	Safety Follow-Up ^{d,e}
	Week	W14	W16	W18	W22	W24	W26	W30	W32	W34		
Study Procedure^{a,b}												
Antibodies to guselkumab/golimumab		X				X			X		X	X
Pharmacodynamics and Biomarkers												
Biopsy (RNA, histology, single cell isolation) ¹											X	X
Serum biomarkers ^m											X	X
Whole blood (RNA) ^m											X	X
Whole blood (PBMC) ^{m,q}											X	X
Fecal biomarkers ⁿ											X	X

CRP=C-reactive protein; C-SSRS=Columbia-Suicide Severity Rating Scale; Early Term=early termination visit; IBDQ=Inflammatory Bowel Disease Questionnaire; PBMC= peripheral blood mononuclear cell; PK=pharmacokinetic; PGIC=Patient’s Global Impression of Change (of Severity of UC); PRO=patient-reported outcome; PROMIS=Patient-Reported Outcomes Measurement Information System; RNA=ribonucleic acid; TB=tuberculosis; UC=ulcerative colitis; W=Week.
 
a. Visit dates are based on the participant’s original randomization date; visit windows are as follows: day of the scheduled visit ±4 days (ie, plus or minus 4 days).
 
b. All assessments are to be completed before study intervention administration, unless otherwise specified; PRO assessments should be completed first. When blood samples are to be collected for safety, PK, efficacy, and biomarkers evaluations at the same time point, the order of blood draws will be samples for CRP, hematology and chemistry, PK/immunogenicity, serum biomarkers, and whole blood RNA.
 
c. Participants who discontinue study intervention or terminate study participation after Week 12 should undergo the procedures indicated for an Early Term visit.
 
d. Participants, including those who discontinue study intervention administration (but have not terminated study participation), will have a final safety follow-up visit approximately 16 weeks after the last administration of study intervention.
 
e. At their last study visit, each study participant will be invited to complete an Independent Ethics Committee/Institutional Review Board approved Experience Survey, to share to his/her experience as a volunteer in this study. The responses will be collected by an external party and provided anonymously to the sponsor.
 
f. Endoscopy findings will be assessed by the investigator (ie, local endoscopist) during the procedure and a video of the endoscopy must be submitted to the central reader.
 
g. If TB is suspected at any time, a chest radiograph (or chest CT scan if obtained instead) and QuantiFERON[®]-TB test should be performed. In countries where the QuantiFERON[®]-TB test is not registered/approved or the tuberculin skin test is mandated by local health authorities, TB skin testing (see Appendix 3 [Section 10.3]) should also be performed. Note: In Ukraine, while the QuantiFERON[®]-TB test is not approved/registered, it is accepted and a tuberculin skin test is not required.
 
h. Temperature, pulse/heart rate, respiratory rate, and blood pressure. At a study intervention administration visit, vital sign measurements should be obtained before and approximately 30 minutes after study intervention administration or if the participant reports any symptoms.
 
i. Must be performed before any study intervention administration for female participants of childbearing potential.
 
j. The C-SSRS should be completed after all PROs and before any other tests, procedures, or other consultations to prevent influencing participant perceptions.
 
k. Samples should be collected before any study intervention administration. All reasonable attempts should be made to collect samples at the scheduled timepoints and record the actual dates and times of PK sample collections.
												

Table 2: SoA- Monotherapy Phase (ie, after Week 12)												
Phase	Treatment										Early Term^{c,e}	Safety Follow-Up^{d,e}
Week	W14	W16	W18	W22	W24	W26	W30	W32	W34	W38		
Study Procedure^{a,b}												

l. Mucosal biopsy samples will be collected from all participants during endoscopy for RNA expression analysis, histologic assessment, and single cell isolation.
 
m. Serum biomarkers and whole blood RNA and PBMCs will be collected from all participants to evaluate the molecular effects of each study intervention in UC.
 
n. Fecal biomarkers (including microbiome) and associated products analysis will be collected from all participants to evaluate the association between microbial activities, study intervention, and/or UC.
 
o. Certain laboratory abnormalities require re-testing and potential discontinuation of study intervention (See Sections 8.2.5 and 7.1, respectively).
 
p. An injection-site reaction is any adverse reaction at any SC study intervention injection site. Injection sites will be evaluated for reactions and any injection-site reaction should be recorded as an adverse event.
 
q. Whole blood (PBMC) samples are to be collected ideally within ± 2 days of the endoscopy visit.
												

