3.1.2. Secondary Objectives

Combination Comparison Phase

- To evaluate the effect of combination therapy with guselkumab and golimumab on endoscopic improvement.
- To evaluate the impact of combination therapy with guselkumab and golimumab on disease-specific health-related quality of life (HRQOL), including fatigue.
- To evaluate the efficacy of combination therapy with guselkumab and golimumab by negative response signature status at baseline.
- To evaluate the PK, immunogenicity, and PD of combination therapy with guselkumab and golimumab, including changes in C-reactive protein (CRP), fecal calprotectin, and other PD biomarkers.

Monotherapy Phase

- To evaluate the clinical efficacy of combination therapy followed by guselkumab monotherapy.
- To evaluate the safety of combination therapy followed by guselkumab monotherapy.
- To evaluate the effect of combination therapy followed by guselkumab monotherapy on endoscopic improvement.
- To evaluate the impact of combination therapy followed by guselkumab monotherapy on disease-specific HRQOL, including fatigue.

- To evaluate the efficacy of combination therapy followed by guselkumab monotherapy by negative response signature status at baseline.
- To evaluate the PK, immunogenicity, and PD of combination therapy followed by guselkumab monotherapy, including changes in CRP, fecal calprotectin, and other PD biomarkers.

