Planned biomarker analyses may be deferred if emerging study data show no likelihood of providing useful scientific information. Any biomarker samples received by the contract vendor or sponsor after the cutoff date will not be analyzed, and therefore, will be excluded from the biomarker analysis.

Changes in serum protein analytes, fecal biomarkers, and biopsy and whole blood RNA obtained over time will be summarized by treatment group. Associations between baseline levels and changes from baseline in select markers and response to treatment will be explored. Biomarker analyses will be summarized in a separate technical report.

The biomarker analyses will characterize the effects of guselkumab and/or golimumab to identify biomarkers relevant to treatment, and to determine if these biomarkers can predict response to guselkumab or golimumab. Results of serum, stool, whole blood, and mucosal biopsy analyses will be reported in separate technical reports.

Pharmacogenomic Analyses

Genetic (DNA) analyses will be conducted only in participants who sign the consent form to participate in the pharmacogenomic sub-study. These analyses are considered exploratory and will be summarized in a separate technical report.

Medical Resource Utilization Analyses

Medical resource utilization data will be descriptively summarized by intervention group.

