2.3. Definition of Subgroups

The primary endpoint will be evaluated for subgroups based on demographics and baseline UC clinical disease characteristics, UC-related concomitant medication usage, and UC-related medication history.

Demographics

- Gender (male, female)
- Race (Caucasian, non-Caucasian)
- Baseline age (\leq median age, $>$ median age)
- Baseline body weight (\leq 1st quartile, $>$ 1st quartile and \leq 2nd quartile, $>$ 2nd quartile and \leq 3rd quartile, $>$ 3rd quartile)
- Baseline body mass index (BMI) (\leq 1st quartile, $>$ 1st quartile and \leq 2nd quartile, $>$ 2nd quartile and \leq 3rd quartile, $>$ 3rd quartile)
- Tobacco use status (non-user, prior user, current user)
- Region
 - Eastern Europe: Poland, Russia, Ukraine
 - Latin America: Argentina, Mexico, Brazil
 - Rest of World: United States, Germany, Australia

Baseline UC clinical disease characteristics

- UC disease duration (\leq 5 years, $>$ 5 years to \leq 15 years, $>$ 15 years)
- Extent of disease (limited, extensive)
- Severity of UC disease (moderately active: $6 \leq$ Mayo score \leq 10, severely active: Mayo score $>$ 10)
- Severity of endoscopic disease (moderate: endoscopic subscore = 2, severe: endoscopic subscore = 3)
- CRP (\leq 3 mg/L, $>$ 3 mg/L)
- CRP (\leq 1st quartile, $>$ 1st quartile and \leq 2nd quartile, $>$ 2nd quartile and \leq 3rd quartile, $>$ 3rd quartile)
- Fecal calprotectin (\leq 250 mg/kg, $>$ 250 mg/kg)

- Fecal calprotectin (\leq 1st quartile, $>$ 1st quartile and \leq 2nd quartile, $>$ 2nd quartile and \leq 3rd quartile, $>$ 3rd quartile)

Baseline UC-related concomitant medications

- Oral 5-aminosalicylic acid [5-ASA] compounds (receiving, not receiving)
- Oral corticosteroids including budesonide and beclomethasone dipropionate (receiving, not receiving)
- Participants taking conventional immunomodulators (6-MP/AZA/MTX) during Screening but discontinuing it prior to Week 0
- Participants taking Vedolizumab during Screening but discontinuing it prior to Week 0

UC-related medication history

- Refractory or intolerant to 6-MP/AZA (yes, no)
- Refractory, dependent or intolerant to oral or IV corticosteroids (yes, no)
- Refractory, dependent, or intolerant to oral or IV corticosteroids, but not refractory or intolerant to 6-MP/AZA (yes, no)
- Refractory, dependent or intolerant to oral or IV corticosteroids, and refractory or intolerant to 6-MP/AZA (yes, no)
- Refractory or intolerant to Vedolizumab (yes, no)

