2.5. Baseline

Baseline is defined as the last observation prior to or on the day of the first study intervention, unless otherwise specified.

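### Serum biomarkers and whole blood RNA have only a loosely timed screening sample as baseline, so within-arm change can include washout and up to 8 weeks of disease drift

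*Protocol*

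**What the plan says.** - **Schedule.** In Protocol 1.3, Table 1, the rows "Serum biomarkers ^w" and "Whole blood (RNA) ^w" are marked at Screening, W2, W4 and W12. W0 is blank. CRP, fecal calprotectin and fecal biomarkers each have a W0 sample.
- **Timing within screening.** Footnote a says "Screening should occur within 8 weeks before the W0 visit". Footnotes o and v hold the screening endoscopy and biopsy to within 2 weeks of W0, and footnote cc asks for PBMC blood ideally within 2 days of the endoscopy visit. For serum and RNA, footnote w gives only the purpose: "Serum biomarkers and whole blood RNA and PBMCs will be collected from all participants to evaluate the molecular" effects of each intervention.
- **Background treatment.** Inclusion Criterion 7 (Protocol 5.1) requires 6-MP, AZA and MTX, rectal and parenteral corticosteroids, and rectal 5-ASA to be stopped at least 2 weeks before the first dose. Criterion 6 requires oral corticosteroid doses to have been stable for at least 2 weeks. SAP 2.3 names a subgroup: "Participants taking conventional immunomodulators (6-MP/AZA/MTX) during Screening but discontinuing it prior to Week 0".
- **Baseline rule.** SAP 2.5: "Baseline is defined as the last observation prior to or on the day of the first study intervention", unless otherwise specified. SAP Section 8 (Biomarkers) specifies nothing different.
- **Use.** The pharmacodynamic secondary objective (Protocol 3.1.2) covers PK, immunogenicity and PD, "including changes in C-reactive protein (CRP), fecal calprotectin, and other PD biomarkers". Protocol 9.4.3 states: "Changes in serum protein analytes, fecal biomarkers, and biopsy and whole blood RNA obtained over time will be summarized by treatment group". It also plans to relate baseline levels and changes from baseline to response.

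**The concern.** A change from baseline reads as an effect of treatment only if the baseline describes the participant as they were when treatment began. Here the reference sample may be weeks older than the first dose and may have been taken on a background regimen that was then withdrawn. Every later sample is taken after that withdrawal. There is no placebo arm (Protocol 2.3), so nothing in the trial shows how much of a within-arm change comes from washout or from natural fluctuation in disease activity.

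The early samples are the most exposed. W2 and W4 are meant to show the first molecular effects, yet time on drug may be a minority of the interval they cover. The serum and RNA baselines may also not be contemporaneous with the W0 CRP, calprotectin and Mayo score to which they would naturally be related.

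**Working it through.** The plan states no figure on this point, so there is none to reproduce.

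**1. Is the table read correctly?** The text was extracted by program, so the columns were checked by tab position against neighbouring rows. The PBMC row reads Screening, (W4), W12, which agrees with the visits named in the Amendment 2 summary. The fecal biomarker row, read the same way, starts at W0. On that alignment the serum and RNA rows have one scheduled pre-dose sample, at Screening.

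**2. Intervals at the 8-week maximum.** Interval = 8 + visit week; on-drug share = visit week / (8 + visit week).

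| Visit | Interval from a W0 baseline | Interval from an 8-week-old baseline | On-drug share |
|---|---|---|---|
| W2 | 2 weeks | 10 weeks | 2/10 = 20% |
| W4 | 4 weeks | 12 weeks | 4/12 = 33% |
| W12 | 12 weeks | 20 weeks | 12/20 = 60% |

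Immunomodulators may be taken until 2 weeks before dosing, that is, for 8 - 2 = 6 of the 8 screening weeks.

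**3. Loss of precision.** The documents give no variance components, so these are assumptions. Let a fraction f of a marker's variance be a component whose within-person correlation over w weeks is rho(w) = r^(w/4), with r from 0.7 to 0.95. The remaining 1 - f is assay or day-to-day noise. The variance of a change over w weeks is then proportional to 1 - f x rho(w).

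Ratio for W2 (10 weeks against 2) = [1 - f x rho(10)] / [1 - f x rho(2)]:

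- No noise (f = 1): r = 0.7 gives (1 - 0.410)/(1 - 0.837) = 3.61; r = 0.95 gives 4.75.
- 10% noise (f = 0.9): r = 0.7 gives 0.631/0.247 = 2.55; r = 0.95 gives 0.208/0.123 = 1.70.
- 20% noise (f = 0.8): 1.35 to 2.03.
- 30% noise (f = 0.7): r = 0.7 gives 0.713/0.414 = 1.72; r = 0.95 gives 0.384/0.318 = 1.21.

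Ratio for W12 (20 weeks against 12): 1.15 to 1.36 with 10-30% noise, and 1.27 to 1.59 with none.

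**4. Which comparisons are affected?** The screening sample precedes randomization, so its age and the regimen at sampling are balanced across arms on average. Between-arm differences in change are unbiased in expectation but carry the extra variance. Within-arm change also absorbs any mean shift from washout or drift; the documents give no size for that shift.

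**The case against.** The strongest reply has five parts.

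- **A W0 serum source exists.** Footnote t requires a pre-dose W0 blood sample, Protocol 8.5.1 splits it into aliquots including a back-up, and Protocol 8.5 allows that serum to be used for relevant biomarkers. This stands for serum, as an option. It is not the designated baseline and cannot supply RNA.
- **The analyses are exploratory.** Protocol 8.8 says so, results go to separate technical reports, and Protocol 9.4.3 allows planned biomarker analyses to be deferred. The two PD markers named in the secondary objective, CRP and fecal calprotectin, have W0 samples. This stands and limits the weight of the point.
- **The main contrast is between arms.** Protocol 8.8 compares combined with single blockade, and that contrast is unbiased. Even with a W0 baseline, within-arm change would still include fluctuation after W0 and the corticosteroid taper from Week 6. This stands: a later baseline reduces the problem but does not remove it.
- **Screening timing may be meant to pair blood with biopsy.** That is plausible but not secured. Section 8 stages screening, with a partial Mayo score first and endoscopy only for those scoring at least 3, so an early blood draw can precede the biopsy by weeks.
- **The actual timing is unknown.** Collection instructions are in a Laboratory Manual that is not among the documents, and the SAP subgroup gives no count. This stands: 8 weeks is a ceiling, not an expected gap.

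Footnote b lists serum biomarkers and RNA in the blood-draw order around the Week 0 DNA sample. It sets an order only and does not schedule a W0 biomarker draw.

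**Conclusion.** The point holds as a limited design weakness in exploratory analyses. The scheduled baseline for serum biomarkers and whole blood RNA may be up to 8 weeks old and taken on immunomodulators that are later withdrawn. Within-arm change can therefore mix drug effect with washout and drift, and between-arm contrasts are noisier than they need be.

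At the maximum gap, the variance of change to W2 is about 1.2 to 2.55 times that with a W0 baseline, assuming r = 0.7 to 0.95 per 4 weeks and 10-30% noise. For W12 it is about 1.15 to 1.6 times across the noise range including zero. Shorter gaps give smaller losses.

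Three stronger readings are tempting but unsupported:

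- **That treatment comparisons are biased.** Randomization balances the screening conditions in expectation, and neither the primary nor the major secondary endpoint uses these samples.
- **That variance rises 3.6- to 4.8-fold.** This needs the full 8-week gap and no assay or day-to-day noise at all.
- **That no W0 serum is available.** The PK back-up aliquot could serve, though only for serum and only if it is used for this purpose.

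**What to change.** **Participants not yet randomized.** In Table 1, move the Screening mark for both rows to W0, before dosing. At minimum, add a footnote tying the screening draw to the endoscopy, and so to within 2 weeks of W0. Leave PBMC and biopsy as they are.

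**Participants already enrolled.** SAP Section 3 reports that the first 126 randomized participants had completed Week 12 or terminated before it by April 2020, so the analysis remedy carries most of the weight:

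- record for each participant the interval from sample to W0 and immunomodulator status at sampling;
- use the W0 PK back-up serum as the serum baseline where feasible;
- repeat the change-from-baseline summaries excluding baselines older than 2 weeks or taken on immunomodulators.

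**Cost.** Two schedule rows and the laboratory kits change. The number of tubes and the blood volume do not: blood is already drawn at W0, and footnote b already sets the draw order. With the W0 option, blood is drawn 4 to 14 days after the screening biopsy, which rules out same-day pairing; the current text does not guarantee that pairing. A mid-study change also creates two baseline timings, which must be flagged in the analysis. The endoscopy-tied option keeps blood and biopsy closer but leaves a gap of up to 2 weeks before dosing.
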